10.1 Follow Up of Grade 3 or 4 Toxicities

Grade 3 or 4 toxicities are to be followed by re-evaluation every 2 days, as feasible, until the toxicity returns to Grade ≤ 2 severity.

10.2 Infection Follow Up

Any new infection that occurs on study regardless of infecting agent (i.e., viral or non-viral) should be captured. Additionally, the site of infection and source of culture (BAL, tracheal aspirate, sputum, blood, urine, etc.) should also be recorded.

10.3 Classification of Causality

Attribution is the relationship between an adverse event or serious adverse event

and the study treatment. Attribution will be assigned as follows:

- Definite – The AE is clearly related to the study treatment.
- Probable – The AE is likely related to the study treatment
- Possible – The AE may be related to the study treatment.
- Unlikely - The AE is doubtfully related to the study treatment.
- Unrelated - The AE is clearly NOT related to the study treatment

Guidance for assessing causality:

The Investigator will need to determine whether an AE is considered related to (“caused by”) the study drug rather than some underlying condition, for example, COVID-19.

For the purposes of this study, ‘drug related’ shall mean ‘Definite’, ‘Probable’ and ‘Possible’ relationship to drug as determined by the Investigator.

10.4 Classification of Severity

The NIH Division of AIDS (DAIDS) Table for Grading the Severity of Adult and Pediatric Adverse Events, Corrected Version 2.1 (July 2017) will be utilized for AE reporting. All appropriate treatment areas should have access to a copy of the criteria.

AEs that are expected are subject to expedited reporting only if the adverse event varies in nature, intensity or frequency from the expected toxicity information that is provided in the Investigator Brochure.

10.5 Serious Adverse Event (SAE) Reporting

The regulatory definition of an SAE is any untoward medical occurrence or effect that at any dose fulfills one or more of these criteria:

- results in death;
- is life threatening (at the time of the event);
- requires in-patient hospitalization or prolongation of existing hospitalization;
- results in persistent or significant disability / incapacity
- is a congenital anomaly / birth defect;
- or is an event considered medically serious by the Investigator.

Disability is defined as a substantial disruption of a person’s ability to conduct normal life functions.

A life-threatening adverse event is one that places the patient/subject, in the view of the Investigator, at immediate risk of death from the event as it occurred. It does not include an event that, had it occurred in a more severe form, might have caused death.

An unexpected adverse event is any adverse drug event, the nature or severity of which is not consistent with the applicable product information (e.g. IB for an unauthorized investigational product or summary of product characteristics for an authorized product).

Enter only one event as the reason for the SAE on the SAE form. Other non-serious events which did not directly result in the SAE should be detailed in the description section on the SAE form and listed separately as AEs if necessary. For fatal SAEs, report the cause of death as an SAE with a fatal outcome rather than reporting death as the SAE term.

Note that hospitalizations for the following reasons should not be reported as SAEs:

- Routine treatment or monitoring of COVID-19 infection, not associated with any deterioration in condition;
- Elective or pre-planned treatment for a pre-existing condition that is unrelated to the indication under study and has not worsened since signing the informed consent;
- Social reasons and respite care in the absence of any deterioration in the subject's general condition;
- Treatment on an emergency outpatient basis that does not result in hospital admission and involves an event not fulfilling any of the definitions of an SAE given above.

ANY SERIOUS ADVERSE EVENT MUST BE REPORTED IMMEDIATELY (WITHIN 24 HOURS) BY EMAIL TO THE SAE REPORTING EMAIL USING THE FORM PROVIDED. ENTER THE SUBJECT'S AVAILABLE INFORMATION INTO THE eCRF WITHIN 48 HOURS.

10.6 Suspected Unexpected Serious Adverse Reactions (SUSARs)

Suspected, unexpected, serious adverse reactions (SUSARs) are SAEs that are both related to the study drug (Relationship = Related) and unexpected (not previously described in the investigator's brochure). All SUSARs will be reported in an expedited manner to the Sponsor or designee and IRB by the Investigators and to all relevant regulatory authorities by the Sponsor. Expectedness will be judged by the Covance Physician and site Investigator. It is critical that all SAEs are reported within the 24-hour guideline so that the expectedness determination can be made. SUSARs require immediate attention and expedited reporting to relevant regulatory authorities.

The Sponsor will ensure that all relevant information about **fatal or life-threatening** SUSARs are appropriately recorded and reported to the concerned Regulatory Authority and to the concerned

IRB(s) within seven (7) calendar days of the date of first report to Covance Patient Safety / Sponsor. Follow-up information will be communicated to the relevant Regulatory Authority within an additional eight calendar days.

All other SUSARs will be reported to the Regulatory Authority and to the IRB(s) concerned as soon as possible within a maximum of fifteen calendar days of first notification to Covance Patient Safety / Sponsor.

The Sponsor or designee will also inform all Investigators studying the investigational medicinal product about SUSARs and ensure that all IRBs have been notified.

For reported deaths of a subject, the Investigator shall supply the Sponsor and the IRB(s) with requested additional information on an expedited basis.

10.7 Pregnancies

Pregnancy occurring in a female subject or a subject's partner during the study period will be documented in the subject's source documents and reported to Covance Patient Safety (by email to [contact]) and to the IRB by the investigational staff within 1 working day of their knowledge of the event. The collection period for a pregnancy occurring in a subject or a subject's partner will begin at the first dose of study drug and will continue through 90 days after the last dose of study drug. Monitoring of the subject or partner should continue until the conclusion of the pregnancy, if the subject or subject's partner has consented to this. Monitoring of the baby should continue for 3 months after birth, if the subject or subject's partner has consented to this.

Pregnancy itself is not an AE; it should be reported for tracking purposes. The Investigator or designee will discontinue the pregnant subject from the treatment aspects of the study, continue to follow her per protocol for safety outcomes only, and advise her to seek prenatal care and counseling from her primary care provider. Data on fetal outcome and breast-feeding will be collected for regulatory reporting and drug safety evaluation, if the subject has consented to this.

If the pregnancy is due to a subject's failure to comply with the contraceptive requirements of this protocol, this should be documented as a protocol deviation.

Complications of pregnancy or congenital abnormalities in the newborn child will be reported appropriately as (S)AEs.

The site clinical staff will request the pregnant subject to notify the site of the outcome of the pregnancy (i.e., birth, loss, or termination). To help ensure this, the site clinical staff will follow the subject until the end of pregnancy, with the subject's consent. This request and the subject's response will be documented in the subject's source document.

10.8 Safety Monitoring for Hematologic Toxicities

Myelosuppression is a known effect of DHODH inhibition that is associated with prolonged exposure and high doses. To reduce the risk of this effect with brequinar in COVID-19 subjects, the extensive brequinar safety database with over 1,000 patients has been evaluated to select a dose level expected to be safe and well tolerated with regard to hematologic toxicity. In addition to enhancing safety by

selecting a relatively brief 5-day exposure and a low brequinar dose, all subjects in the clinical trial will be under the care of highly qualified medical personnel. Clinically significant out-of-range laboratory results will be reported as adverse events.

In addition to real time assessments by the treating clinical team, the Covance Medical Monitor will assess the available hematology data on a periodic basis to identify any pathologic trends or safety issues. Any apparent increase in the expected rate or severity of hematologic safety events will be discussed with the Principal Investigators and the Sponsor. In addition, the Data Monitoring Committee (DMC) will assess available hematology data on a periodic basis to independently assess any pathologic trends or safety issues. If the rate or severity of hematologic toxicities appears to be above the expected rate or the severity appears worse than that expected, the trial enrollment will be suspended and no further subjects will be treated while a comprehensive data review is conducted. Depending on the outcome of the safety review the study may be stopped, the design adjusted, or the study may continue as designed. Individual and Study stopping rules are provided in [Section 8.4](#).

Safety laboratory results are to be initially assessed in real time by the Principal Investigator or designated person. Any study drug-related clinically significant out-of-range laboratories or study drug-related adverse events will be followed as needed until resolution or stable.

The in-clinic assessments and telemedicine/phone call visits will specifically ask about possible hematologic toxicity including any evidence of the list below. Subjects will be provided with a list of the following events in lay terms and will be instructed to call the research team if any of these events occur.

- Ecchymosis/purpura/petechiae
- Epistaxis
- Hemoptysis
- Hematuria
- Gingival bleeding
- Prolonged bleeding time from needle sticks, abrasions or lacerations
- Hematemesis
- Rectal bleeding
- Blood in stool
- Any other unusual bleeding noted by the subject or caregiver

Any of these symptoms considered clinically significant will be recorded as an adverse event and must be followed until resolved or stable.

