As much of the study as possible will be conducted via telemedicine remote from the site (e.g., consent, medical history, concomitant medications may be collected remotely). Subjects will be visited at home (or place of residence) by a home health nurse or come to the site for an in-person visit at Screening and on study Day 1. The subjects will be visited at home for Study Days 8, 15, and 29. On study Days 4, 12, and 22 the vital signs and saliva collections will be observed via telemedicine by the study site staff. Site staff will have a telephone call with subjects on study days 2, 3, 5, 6, and 7 to assess changes in concomitant medications and to assess adverse events, especially those that may indicate thrombocytopenia, e.g., unusual bruising, epistaxis, gingival bleeding, etc., and mucositis. Subjects will be provided with a pulse oximeter and thermometer during the Screening or Day 1 visit, as well as being trained on the use of these devices during the visit. Training will also be provided for the saliva collection required for viral load testing. Assessments will be recorded by the study staff during home and clinic visits and by the site staff during telemedicine visits. These data will be entered in the eCRF by the site staff or as determined by the study team.

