10 ADVERSE EVENT REPORTING

An adverse event is any untoward medical occurrence in a patient or clinical trial subject administered a medicinal product and which does not necessarily have a causal relationship with this treatment. An AE can therefore be any unfavorable and unintended sign (including an abnormal laboratory finding), symptom, or disease temporally associated with the use of the medicinal product, whether or not considered related to the medicinal product.

Events that occur prior to first dose will be entered as medical history; events that occur after first dose will be entered as adverse events (AEs) on the AE form.

Subjects will be questioned and observed for evidence of AEs, whether or not judged by the Investigator or designated person to be related to study drug. All AEs will be documented in the subject's medical record and CRF. For any pre-existing condition or abnormal laboratory finding that changes in severity after dosing, this change should be recorded as an AE. New abnormal laboratory findings that are clinically significant are considered AEs. Investigators and site staff are to elicit from the subject and note any signs or symptoms of mucositis and thrombocytopenia (see Section 10.8).

Adverse events will be collected from the time of first dose through Day 29. After Day 29, collect/record only Serious Adverse Events (SAEs) which are assessed by the Investigator or designated person to be related to study drug and have an onset within 14 days of study completion (Day 29 or earlier if discontinue prior to Day 29). AE details are to be documented including start and stop date and times, whether continuous or intermittent, severity, any intervention utilized to correct the event (e.g., medication, surgery, or other therapy), outcome and the relationship to the study drug.

AEs identified in the protocol as critical to the evaluation of safety must be reported to the Sponsor by the Investigator according to the reporting requirements within the time periods specified in the protocol.

AEs determined by the Investigator to be related to study drug must be followed until resolution or until they are considered stable or for at least 30 days after discontinuation of study drug.

Abnormal laboratory values or test results occurring after study enrollment constitute AEs only if they induce clinical signs or symptoms, are considered clinically significant, are Grades 3 or 4, or require therapy.

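### Protocol Section 10.8 ties AE recording of elicited bleeding signs to an undefined clinical-significance judgement that Section 10 does not apply, so low-grade bleeding could be under-counted in the AE data

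*Protocol*

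**What the plan says.** Protocol Section 10.8 lists ten bleeding signs, from petechiae and epistaxis to a catch-all for other unusual bleeding. On eliciting them it says: "The in-clinic assessments and telemedicine/phone call visits will specifically ask about possible hematologic toxicity including any evidence of the list below". Section 9.4 gives the calls on Days 2, 3, 5, 6 and 7 the same emphasis: "to assess adverse events, especially those that may indicate thrombocytopenia, e.g., unusual bruising, epistaxis, gingival bleeding, etc., and mucositis". On recording, the closing sentence of 10.8 reads: "Any of these symptoms considered clinically significant will be recorded as an adverse event and must be followed until resolved or stable".

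Section 10 sets the general rule. Its definition is broad: "An AE can therefore be any unfavorable and unintended sign (including an abnormal laboratory finding), symptom, or disease temporally associated with" use of the product. It continues that "events that occur after first dose will be entered as adverse events (AEs) on the AE form", and that "All AEs will be documented in the subject's medical record and CRF". It also tells staff to ask for and note any sign of mucositis or thrombocytopenia, referring to 10.8, but does not say where to note it. Section 10 does restrict laboratory findings: "Abnormal laboratory values or test results occurring after study enrollment constitute AEs only if they induce clinical signs or symptoms", or meet one of a few further conditions. It places no such restriction on symptoms.

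SAP Section 7.7.2 codes and tabulates the AEs recorded on the eCRF. SAP Section 7.7.3 summarizes platelets by visit and counts abnormal laboratory results under both headings, clinically significant and not.

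**The concern.** The signs the trial most wants to hear about appear to face a higher recording threshold than any other symptom. Suppose a subject mentions a single nosebleed on the Day 3 call. Under Section 10 it is an AE. Under 10.8 a coordinator could judge it minor and leave it off the form. With about 15 sites and no definition, that judgement may vary.

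At stake are three uses of the AE data:

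- the secondary endpoint of AE and SAE rates (Protocol Section 6.2), which carries no grade limit;
- the AE listings the DMC reviews (Section 10.9);
- the provision in 10.8 to suspend enrollment if hematologic toxicity looks more frequent or more severe than expected, which also has no grade limit.

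**Working it through.** The plan states no figure for bleeding, so there is none to reproduce. The check is a comparison of texts, followed by an illustration on assumed rates.

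**1. Do the two sections conflict?**

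| Question | Section 10 | Section 10.8 |
|---|---|---|
| Which events go on the AE form? | Any sign or symptom after first dose | The listed signs judged clinically significant |
| Is there a filter on symptoms? | None; the restrictive wording covers laboratory values | Clinical significance, undefined, no assessor named |
| Where does a sign go if not entered as an AE? | To be noted, place not stated | Not stated |

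They do. If every elicited sign is recorded anyway, the qualifier has no function in the recording half of the 10.8 sentence. If it has a function, it contradicts Section 10.

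**2. Does any other output catch a sign left off the form?** SAP 7.7.2 works from AEs on the eCRF, and the SAP has no bleeding listing or table. The symptom assessment is directed at COVID-19 symptoms, and its examples in the Schedule of Events include no bleeding item. No other planned output was found.

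**3. What other platelet information is there?** Hematology is scheduled at Screening, Day 1, Day 8 and Day 15; the Day 1 draw is not repeated if one was taken within 48 hours. Dosing runs from Day 1 to Day 5. No draw is scheduled between Day 1 and Day 8, so in that interval the answers to these questions are the only scheduled platelet-related information. Unscheduled tests to assess AEs are allowed (Section 9.5.1).

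**4. Illustration of size.** Inputs: n = 50 brequinar subjects (Section 7.1); p = true proportion with a mild sign, assumed 10% or 20%; f = share judged clinically significant and recorded, assumed. Neither p nor f is in the documents.

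Expected recorded subjects = n × p × f. P(at least 3 recorded) is the upper tail of a binomial with n = 50 and probability p × f. Three is an arbitrary marker of a visible cluster.

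| p | f | Expected | P(at least 3) |
|---|---|---|---|
| 10% | 100% | 50 × 0.10 × 1 = 5.0 | 0.89 |
| 10% | 75% | 3.75 | 0.73 |
| 10% | 50% | 2.5 | 0.46 |
| 10% | 25% | 1.25 | 0.13 |
| 20% | 100% | 10.0 | above 0.99 |
| 20% | 75% | 7.5 | 0.99 |
| 20% | 50% | 5.0 | 0.89 |
| 20% | 25% | 2.5 | 0.46 |

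With an assumed 2% in the placebo arm against 10%, a recording share of 50% in both arms gives expected counts of 2.5 against 0.5 instead of 5 against 1. The difference falls from 8 to 4 percentage points.

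**The case against.** The strongest reply is that 10.8 does not say only. Section 10 states the general rule more than once, and the v5.0 synopsis lists the same signs under AE assessment with no filter. Where the protocol wants an exclusive condition, as for laboratory values, it writes one. On that reading 10.8 merely adds follow-up for the more important signs. This stands as far as it goes: a reader might infer that the protocol excludes mild bleeding by rule, and the text does not support that. It does not remove the conflict, because the qualifier is attached to recording as well as to follow-up, and Section 10 itself sends staff to 10.8.

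A reader might also infer that platelet suppression would go unseen. It would not. Platelets are summarized at each scheduled draw regardless of significance, the DMC reviews safety laboratory data, and the medical monitor reviews hematology periodically. Day 8 falls three days after the last dose. Subjects are also told to call if a listed sign occurs.

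The consequence is bounded too. The safety objective in Section 4.2 is framed on Grade 3 and 4 AEs and SAEs, and the pause rules in Section 8.4.2 count related Grade 3-4 events; missing mild signs changes neither. Judgements are made blind, so there is no reason to expect the filter to favor an arm. Blinding does not, however, prevent the loss of counts in both arms or the shrinkage of an absolute difference shown above.

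Finally, it is tempting to size the loss against the 5.1% (2 of 39) with related Grade 3-4 events in Section 8.2.1. Those events were hyperbilirubinemia and hyperglycemia, so they say nothing about mild bleeding.

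**Conclusion.** The point holds as an unreconciled conflict over recording, with an undefined term at its center. A site following 10.8 may omit low-grade bleeding that Section 10 requires on the AE form, and nothing planned in the SAP would recover it. The AE tables, the AE data before the DMC and the ungraded suspension provision in 10.8 could then rest on an under-count. Platelet summaries and the Grade 3-4 pause rules are untouched.

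The size is unknown: the documents give neither a rate of mild bleeding nor the share sites would consider significant, and the figures above only show how the loss scales under assumed values. Nor do the documents call these signs early markers of the drug's main toxicity. Section 9.4 says only that they may point to thrombocytopenia, which Section 3.6 names alongside mucositis as dose-limiting on a high-dose weekly schedule. The change is still worth making, because the protocol contradicts itself on events it singles out for attention and the correction is small.

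**What to change.** Reconcile 10.8 with Section 10 by splitting the closing sentence of 10.8 in two. The recording sentence should say that every listed sign elicited at a study contact, if new or worse since first dose, is entered as an AE with its DAIDS grade and causality. The existing follow-up clause then stands as its own sentence; if the sponsor keeps the clinical-significance qualifier, it belongs there only.

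Deleting the qualifier from the present sentence would not do, because that sentence also carries the follow-up requirement and the deletion would make follow-up compulsory for every trivial sign.

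The cost is a one-sentence protocol amendment and a memo to sites. The SAP needs no new output, since the events would enter its existing AE tables by severity and relationship. The downside is more Grade 1 AEs in both arms.

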10.9 Data Monitoring Committee

A Data Monitoring Committee (DMC) will be established to provide independent oversight to this trial. The primary responsibility of the DMC will be to review the progress and conduct of the trial in order to maintain scientific rigor and to ensure the wellbeing of subjects participating in the trial. The specific responsibilities of the DMC will be detailed in a separate DMC charter. The DMC will include at a minimum at least one statistician and two clinicians who will perform periodic data review to assess whether there are clinically significant differences between treatment arms that could affect participant safety. All adverse events will be reviewed by the DMC during their reviews. Following

such a review, the DMC Chair will advise the Sponsor that the study be stopped, the design changed, or that the study may continue per protocol.

